10.4 Expedited Adverse Event Reporting Requirements for IND/IDE Agents

10.41 Expedited Reporting via the **ACCRU Adverse Event Expedited Report Form** for Adverse Events That Occur Within 30 Days¹ of the Last Dose of the Investigational Agent**FDA REPORTING REQUIREMENTS FOR SERIOUS ADVERSE EVENTS (21 CFR Part 312)**

NOTE: Investigators **MUST** immediately report to the sponsor **ANY** Serious Adverse Events, whether or not they are considered related to the investigational agent(s)/intervention (21 CFR 312.64)

An adverse event is considered serious if it results in **ANY** of the following outcomes:

- 1) Death
- 2) A life-threatening adverse event
- 3) An adverse event that results in inpatient hospitalization or prolongation of existing hospitalization for ≥ 24 hours
- 4) A persistent or significant incapacity or substantial disruption of the ability to conduct normal life functions
- 5) A congenital anomaly/birth defect.
- 6) Important Medical Events (IME) that may not result in death, be life threatening, or require hospitalization may be considered serious when, based upon medical judgment, they may jeopardize the patient or subject and may require medical or surgical intervention to prevent one of the outcomes listed in this definition. (FDA, 21 CFR 312.32; ICH E2A and ICH E6).

ALL SERIOUS adverse events that meet the above criteria **MUST** be immediately reported to the sponsor within the timeframes detailed in the table below.

Hospitalization	Grade 1 and Grade 2 Timeframes	Grade 3-5 Timeframes
Resulting in Hospitalization ≥ 24 hrs.	7 Calendar Days	24-Hours; 1 Calendar Day
Not resulting in Hospitalization ≥ 24 hrs.	Not required	

Note: Protocol specific exceptions to expedited reporting of serious adverse events are found in section 10.32

Expedited AE reporting timelines are defined as:

- "24-Hour; 1 Calendar Day" - The AE must initially be reported within 24 hours of learning of the AE, followed by a complete expedited report within 3 calendar days of the initial 24-hour report.
- "7 Calendar Days" - A complete expedited report on the AE must be submitted within 7 calendar days of learning of the AE.

¹Serious adverse events that occur more than 30 days after the last administration of investigational agent/intervention and have an attribution of possible, probable, or definite require reporting as follows:

Expedited 24-hour notification followed by complete report within 3 calendar days for:

- All Grade 3, 4, and Grade 5 AEs

Expedited 7 calendar day reports for:

- Grade 2 AEs resulting in hospitalization or prolongation of hospitalization

² For studies using PET or SPECT IND agents, the AE reporting period is limited to 10 radioactive half-lives, rounded UP to the nearest whole day, after the agent/intervention was last administered. Footnote "1" above applies after this reporting period.

Effective Date: May 5, 2011

- Follow site-specific reporting guidelines.
- Submit the ACCRU Adverse Event Expedited Report Form to the ACCRU SAE Coordinator via fax [REDACTED]. The ACCRU SAE Coordinator will forward to Bristol-Myers-Squibb and Seattle Genetics.
- ACCRU SAE Coordinator will forward to [REDACTED] as appropriate. The ACCRU SAE Coordinator will also fax or e-mail to Seattle Genetics at: Facsimile [REDACTED] or Email: [REDACTED]
- The ACCRU IND Coordinator will assist the sponsor-investigator in notifying the FDA if required.

10.5 Other Required Reporting

10.51 Unanticipated Problems Involving Risks to Subjects or Others (UPIRTSOS) in general, include any incident, experience, or outcome that meets **all** of the following criteria:

1. Unexpected (in terms of nature, severity, or frequency) given (a) the research procedures that are described in the protocol-related documents, such as the IRB-approved research protocol and informed consent document; and (b) the characteristics of the subject population being studied;
2. Related or possibly related to participation in the research (in this guidance document, possibly related means there is a reasonable possibility that the incident, experience, or outcome may have been caused by the procedures involved in the research); and
3. Suggests that the research places subjects or others at a greater risk of harm (including physical, psychological, economic, or social harm) than was previously known or recognized.

Some unanticipated problems involve social or economic harm instead of the physical or psychological harm associated with adverse events. In other cases, unanticipated problems place subjects or others at increased *risk* of harm, but no harm occurs.

Note: If there is no language in the protocol indicating that pregnancy is not considered an adverse experience for this trial, and if the consent form does not indicate that subjects should not get pregnant/impregnate others, then any pregnancy in a subject/patient or a male patient's partner (spontaneously reported) which occurs during the study or within 120 days of completing the study should be reported as a UPIRTSO.

If the event meets the criteria for an UPIRTSO, submit to your IRB as required by your institutional policies.

10.52 ACCRU will provide a study-specific cumulative SAE line listing of all SAEs including an assessment of causality to the Product. This will be e-mailed monthly to Seattle Genetics at: [REDACTED]

10.53 Serious Adverse Event Collection and Reporting

Following the subject's written consent to participate in the study, all SAEs, related or not related to study drug, must be collected, including those thought to

be associated with protocol-specified procedures. All SAEs must be collected that occur after discontinuation of dosing (please refer to test schedule). All SAEs must be collected that occur during the screening period. If applicable, SAEs must be collected that relate to any protocol-specified procedure (eg, a follow-up skin biopsy). The investigator should report any SAE that occurs after these time periods that is believed to be related to study drug or protocol-specified procedure. SAEs, whether related or not related to study drug, and pregnancies must be reported to ACCRU within 24 hours and the ACCRU SAE coordinator will report to BMS within 1 business day. SAEs must be recorded on BMS or an approved form; pregnancies on a Pregnancy Surveillance Form.

10.54 Baseline and Adverse Events Evaluations

Pre-treatment symptoms/conditions to be graded at baseline and adverse events to be graded at each evaluation per the CTCAE v4.0 grading unless otherwise stated in the table below:

System Organ Class	Adverse event/Symptoms	Baseline	Each evaluation
Nervous System Disorders	Peripheral motor neuropathy	X	X
Investigations	Creatinine increased	X	X
Respiratory, thoracic and mediastinal disorders	Pneumonitis	X	X
	Dyspnea	X	X

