1.22 Clinical Experience

The safety and efficacy of brentuximab vedotin has been evaluated in more than^{SEP} 450 patients with HL, sALCL, and other CD30+ hematologic malignancies in 11 clinical studies. Clinical data have been collected from 2 completed phase 1 dose-escalation studies (SG035-0001 and SG035-0002), a pivotal phase 2 study in relapsed or refractory HL after ASCT (SG035-0003), a pivotal phase 2 study in relapsed or refractory systemic ALCL (sALCL) (SG035-0004), and a phase 1 drug-drug interaction study (SGN35-008A). Preliminary and final analyses of safety data indicate that brentuximab vedotin has a manageable safety profile in the studied populations.

1.221 In Study SG035-0001, a total of 45 patients with CD30+ hematologic malignancies (42 with HL, 2 with sALCL, 1 with angioimmunoblastic T-cell lymphoma) were treated with brentuximab vedotin at dose levels of 0.1 to 3.6 mg/kg administered intravenously (IV) every 3 weeks. The primary objectives of the study were to establish a maximum tolerated dose (MTD) of brentuximab vedotin and to assess the associated toxicity profile. The most common adverse events (AEs) were fatigue (36%), pyrexia (33%), diarrhea, nausea, peripheral neuropathy, and neutropenia (22% each). Notable serious adverse events (SAEs) considered at least possibly related to treatment included anaphylaxis, myocardial infarction, and peripheral neuropathy. Numerous responses, including

complete remissions (CRs), were observed. The maximum tolerated dose (MTD) was determined to be 1.8 mg/kg administered IV over 30 minutes every 3 weeks.

- 1.222 In Study SG035-0002, a total of 44 patients with CD30-positive hematologic malignancies (including 38 with HL) were treated with brentuximab vedotin at dose levels of 0.4 to 1.4 mg/kg administered IV weekly for 3 of 4 weeks. The primary objectives explored in this study were to establish the safety profile and MTD of weekly brentuximab vedotin monotherapy in patients with relapsed/refractory CD30+ hematologic malignancies. Brentuximab vedotin (ADCETRIS™) Clinical Study Protocol C25003 Amendment 4, EudraCT: 2011-005450-60

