- 1.223 Although this weekly regimen was designed to enable combination use with gemcitabine, efficacy with brentuximab vedotin monotherapy was deemed sufficient and the planned brentuximab vedotin/gemcitabine combination was not pursued. The most common AEs were peripheral sensory neuropathy (66%); fatigue (52%); nausea (50%); diarrhea (32%); arthralgia (27%); pyrexia (25%); and decreased appetite, myalgia, and upper respiratory tract infection (23% each). Treatment discontinuations due to AEs were observed in 30% of patients. The most frequent AE that led to dose modification or delay was peripheral sensory neuropathy. Acute infusion reaction AEs occurred in a total of 6 patients. Overall, these acute infusion reaction AEs were reported as less than Grade 2 in severity and resolved. Overall, 2 patients (14%) who had an acute infusion reaction also had antitherapeutic antibodies at any postbaseline visit.
- 1.224 In SG035-0003, a phase 2 single-arm, open-label study in patients with relapsed or refractory HL after ASCT, and SG035-0004, a phase 2 trial conducted in patients with relapsed or refractory sALCL, brentuximab vedotin was administered at a dose of 1.8 mg/kg every 3 weeks. One hundred two patients with relapsed and refractory HL and 58 patients with relapsed and refractory sALCL were exposed for a median duration of approximately 27 weeks (9 cycles) and 20 weeks (6 cycles), respectively. Most patients (89%) in the 2 phase 2 studies were between the ages of 18 and 65 years. The primary endpoint of both studies was overall response rate (ORR) as assessed by an independent review facility (IRF). Key secondary endpoints included duration of response, CR rate per IRF, OS, and progression free survival (PFS). The key efficacy results in HL (SG035-0003) include ORR per IRF (75% [95% confidence interval (CI): 64.9-82.6%]), CR rate per IRF (34% [95% CI: 25.2-44.6%]), B symptom resolution rate (77%), and duration of response (DOR) 6.7 months. Of interest, for those patients achieving a CR, the median DOR was 20.5 months. Key efficacy endpoints in sALCL (SG035-0004) include ORR per IRF (88% [95% CI: 74.6-93.9%]), CR rate per IRF (53% [95% CI: 39.6-66.7%]), and B symptom resolution rate (82%).

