- 1.225 Treatment-emergent AEs (TEAEs) occurring in $\geq 20\%$ of patients in phase 2 were peripheral sensory neuropathy (44%), fatigue (42%), nausea (41%), diarrhea (34%), pyrexia (31%), upper respiratory tract infection (28%), neutropenia (21%), and vomiting (20%). These events

were primarily mild to moderate in severity and reversible. Approximately half of patients had treatment-emergent peripheral neuropathy, predominantly sensory neuropathy, with an onset and severity pattern consistent with a cumulative effect. Dose delay and subsequent reduction to 1.2 mg/kg was generally effective in managing peripheral neuropathy. Grade 3 and 4 neutropenia occurred in 13% and 7% of patients, respectively.

Brentuximab vedotin (ADCETRISTM)^[1]_[SEP] Clinical Study Protocol C25003 Amendment 4, EudraCT: 2011-005450-60

- 1.226 These events were typically of short duration and well managed by brief dose delays with growth factor support in some cases. Infusion-related reactions occurred in approximately 10% of patients and were typically managed by dose interruption. Infusion-related reaction prophylaxis in subsequent treatment cycles was instituted at the discretion of the investigator. The clinical laboratory parameters for which the most patients had new or worsening shifts to \geq Grade 3 were low neutrophils (11%), lymphocytes (11%), platelets (6%), leukocytes (5%), and high glucose (6%). Only 1 patient in the phase 2 studies had Grade 3 ALT and aspartate aminotransferase (AST).
- 1.227 In the phase 2 studies, 31% of patients had an SAE, 28% had an SAE of Grade 3 or higher, and 15% had an SAE that was determined by the investigator to be related to brentuximab vedotin. The most common SAE preferred terms (2%) were abdominal pain, disease progression (recurrent sALCL), pulmonary embolism, and septic shock. A higher proportion of sALCL patients experienced SAEs, including deaths within 30 days of last dose, relative to HL patients, likely due to the older age and more aggressive nature of the malignancy in this patient population.

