6.3 Safety Analysis Cohort and Phase II Cohort

6.31 Correlative Research

A mandatory correlative research component is part of this study. The patient will be automatically registered onto this component (see Sections 3.0, 14.0 and 17.0).

6.32 Prior to accepting the registration, registration/randomization application will verify the following:

- IRB approval at the registering institution
- Patient eligibility
- Existence of a signed consent form
- Existence of a signed authorization for use and disclosure of protected health information

6.33 Documentation of IRB approval must be on file in the Registration Office before an investigator may register any patients. Approvals should be uploaded using the online ACCRU Regulatory Management System (ARMS).

In addition to submitting initial IRB approval documents, ongoing IRB approval documentation must be on file (no less than annually) with ACCRU. Approvals should be uploaded using online ACCRU Regulatory Management Systems (ARMS). If the necessary documentation is not submitted in advance of attempting patient registration, the registration will not be accepted and the patient may not be enrolled in the protocol until the situation is resolved.

Submission of annual IRB approvals is required until the study has been closed through your IRB.

- 6.34 At the time of registration, the following will be recorded:
- Patient has/has not given permission to store and use his/her sample(s) for future research to learn about, prevent, or treat cancer.
 - Patient has/has not given permission to store and use his/her sample(s) for future research to learn, prevent, or treat other health problems (for example: diabetes, Alzheimer's disease, or heart disease).
 - Patient has/has not given permission for ACCRU to give his/her sample(s) to outside researchers.
- 6.35 Treatment on this protocol must commence at an ACCRU institution under the supervision of a medical oncologist or hematologist.
- 6.36 Treatment cannot begin prior to registration and must begin ≤ 14 days after registration.
- 6.37 Pretreatment tests/procedures (see Section 4.0) must be completed within the guidelines specified on the test schedule.
- 6.38 All required baseline symptoms (see Section 10.54) must be documented and graded.
- 6.39a Study drug is available on site.
- 6.39b Blood draw kit is available on site. Kits must be used for this study.

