Immune System Disorders	Immune system disorders-other	Nivolumab	
If patient experiences immune-mediated rash Grade 3: Omit nivolumab dose until symptoms resolve and management with corticosteroids is complete, and then restart at the same dose level. If reoccurrence, discontinue nivolumab (continue brentuximab vedotin per protocol).
 
Grade 4: Permanently discontinue nivolumab (continue BV per protocol).
 
For any suspected immune-mediated adverse reactions, exclude other causes. Based on the severity of the adverse reaction, omit nivolumab, administer high-dose corticosteroids, and if appropriate, initiate hormone-replacement therapy. Upon improvement to Grade 1 or less, initiate corticosteroid taper and continue to taper over at least 1 month. Consider restarting nivolumab after completion of corticosteroid taper based on the severity of the event (continue BV per protocol).

Infections and Infestations	Encephalitis infection	Brentuximab Vedotin (BV) and Nivolumab	Discontinue Nivolumab if patient experiences immune-mediated encephalitis. Continue BV at same dose per protocol.

→ → Use the NCI Common Terminology Criteria for Adverse Events (CTCAE) version 4.0* unless otherwise specified ← ←			
CTCAE System/Organ/Class (SOC)	ADVERSE EVENT	AGENT	ACTION**
Nervous system disorders	Peripheral sensory neuropathy or peripheral motor neuropathy	Brentuximab Vedotin (BV)	
Grade 2 Reduce BV by 1 dose level and resume treatment; if already at 1.2 mg/kg, continue dosing at that level.
 
Grade 3 Omit BV until toxicity is ≤ Grade 2, then consult with PI
 
Grade 4 Discontinue BV. Continue Nivolumab at same dose per protocol.

Gastrointestinal disorders	Pancreatitis	Brentuximab Vedotin and Nivolumab	
Grade 2 Omit nivolumab until resolution, maximum 3 weeks. If > 3 weeks, discontinue nivolumab ONLY (continue BV per protocol).
 
Grade 3 or Grade 4, Discontinue BV . Hold nivolumab until grade 1 or better, then reintroduce. If it recurs, then discontinue nivolumab and patient should go to event monitoring, per Section 18.

Gastrointestinal disorders	Diarrhea	Brentuximab Vedotin (BV) and Nivolumab	
Grade ≥2: Hold both BV and nivolumab until resolution to baseline grade
 
Grade 3: Hold both BV and nivolumab and start corticosteroids until resolution to baseline grade.
 
Grade ≥4: Discontinue BV and Nivolumab. Patient should go to event monitoring, per Section 18.

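### Peripheral sensory neuropathy is not in the Section 10.54 list of graded events, so grade 1 events and a baseline grade need not be submitted

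*Combined protocol and SAP*

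**What the plan says.** Section 10.54 introduces its table as "Pre-treatment symptoms/conditions to be graded at baseline and adverse events to be graded at each evaluation per the CTCAE v4.0 grading". Four events follow: peripheral motor neuropathy, creatinine increased, pneumonitis and dyspnea. Under nervous system disorders the single row is "Peripheral motor neuropathy".

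Section 6.38 makes this table the baseline requirement at registration: "All required baseline symptoms (see Section 10.54) must be documented and graded".

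Section 10.55 covers events not specified in Section 10.5. It asks for grade 2 events if at least possibly related, grade 3 and 4 events whatever their attribution, and deaths.

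Elsewhere the protocol treats the sensory form as the main one. Section 1.225 states: "Approximately half of patients had treatment-emergent peripheral neuropathy, predominantly sensory neuropathy". The corresponding row of the Section 8.2 dose-modification table is headed "Peripheral sensory neuropathy or peripheral motor neuropathy".

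**The concern.** The list solicits the less common form of neuropathy and leaves out the predominant one, and no reason is given. Safety and tolerability is a secondary goal (Section 2.22). Section 16.324 analyses it as the maximum grade of each event type per patient, so the result depends on which grades reach the database.

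Two things are at stake. The first is the any-grade rate of sensory neuropathy, which would not be comparable with the 44% that the protocol cites. The second is how to read grade 1 events. Section 3.29d excludes grade 2 or higher neuropathy but admits grade 1. Without a recorded entry grade, a grade 1 event on treatment may be new or may have been there all along.

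**Working it through.** The plan states no figure on this point, so there is none to reproduce. The check is a reading of the collection rules, followed by an illustration of size.

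**Step 1: what must be submitted for sensory neuropathy.** Section 10.55 sets separate thresholds for events not specified in Section 10.5, so the 10.54 table is read as a closed list.

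| Item | Motor neuropathy (listed in 10.54) | Sensory neuropathy (not listed) |
|---|---|---|
| Baseline grade | Required (6.38, 10.54) | Not required |
| Grade 1 on treatment | Required | Not required |
| Grade 2, judged unrelated | Required | Not required |
| Grade 2, at least possibly related | Required | Required (10.551) |
| Grades 3 and 4 | Required | Required (10.552) |

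One small exception: Section 10.41 requires an expedited report of a grade 1 or 2 event that leads to hospitalization of at least 24 hours. This would seldom apply to grade 1 sensory neuropathy.

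**Step 2: what the baseline gap amounts to.** Section 3.29d leaves eligible patients at grade 0 or 1. A reported event of grade 2 or higher is therefore a worsening from baseline. Only the distinction between 0 and 1 at entry is missing.

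**Step 3: how common the event is in the cited studies.**
- Pooled phase 2, 1.8 mg/kg every 3 weeks (Section 1.225): sensory neuropathy 44%, ahead of fatigue 42% and nausea 41%.
- Weekly phase 1 study (Section 1.223): sensory neuropathy 66%, ahead of fatigue 52%.
- Phase 1 study SG035-0001, every 3 weeks (Section 1.221): peripheral neuropathy 22%, behind fatigue 36% and pyrexia 33%.
- SGN35-009, with chemotherapy (Section 1.229b): neuropathy in 25 of 51 patients, of whom one exceeded grade 2. The other 24 stayed at grade 1 or 2. The split between these two grades is not given.

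**Step 4: illustration of size.** Inputs are the 44% from Section 1.225 and N = 56, the evaluable sample in Section 16.2. Let s be the share of affected patients whose worst grade is 1. The documents do not give s, so a range is assumed. It is also assumed that sites submit only what is required, and that no grade 2 event is judged unrelated.

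- Expected patients affected: 56 × 0.44 = 24.6
- Patients not reported: 24.6 × s
- Reported any-grade rate: 0.44 × (1 − s)

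| Assumed s | Not reported | Reported rate |
|---|---|---|
| 25% | 6.2 | 33% |
| 50% | 12.3 | 22% |
| 75% | 18.5 | 11% |

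Section 16.324 counts all eligible patients who started treatment, so the safety denominator may differ from 56. The percentages do not depend on it; the counts would scale with it.

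**The case against.** The strongest case on the other side is that little of importance is lost. Section 4.0 schedules an adverse event assessment at baseline and before each cycle, and Section 15.195 has neuropathy symptoms assessed before each infusion. Related grade 2 and all grade 3-4 events are collected. Sensory neuropathy is a listed toxicity of brentuximab vedotin (Section 15.17), so a grade 2 case would probably be judged at least possibly related. Fatigue and nausea are nearly as common in the phase 2 data and are also unlisted, so not soliciting grade 1 looks like general policy. No decision uses grade 1: neuropathy dose changes begin at grade 2, and the dose-limiting toxicity definition and the adverse event stopping rule require grade 4 or higher.

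Most of this stands, and it limits the point to grade 1, grade 2 judged unrelated, and the entry grade. It does not remove the point. Sections 4.0 and 15.195 require that the patient be assessed, not that a grade 1 finding or an entry grade be submitted. The general-policy argument does not explain why motor neuropathy is solicited at all grades and the sensory form is not.

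Some stronger readings are tempting but unsupported:
- *Sensory neuropathy has no baseline at all.* Section 3.29d bounds it at grade 0 or 1.
- *Grade 1 events will never be recorded.* The case report forms are not among the documents, and sites may record more than the minimum. What can be said is that submission is not required.
- *Time to onset would be understated.* If grade 1 is missed, the first recorded event comes later, so onset would appear delayed. Section 16.324 does not plan such an analysis.
- *It is the most frequent toxicity throughout the cited studies.* That fails for SG035-0001.

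**Conclusion.** The gap is real but narrow. As written, Sections 6.38, 10.54 and 10.55 together do not require submission of grade 1 sensory neuropathy, grade 2 sensory neuropathy judged unrelated, or an entry grade. If sites follow the minimum, any-grade incidence will be understated. If some submit grade 1 events anyway, new and pre-existing ones cannot be separated.

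The figure of about 6 to 18 unreported patients out of about 25 affected rests on the cited 44% carrying over to this population and on an assumed grade 1 share of 25% to 75%. It shows scale and is not a forecast. Dose-limiting toxicity counts, the adverse event stopping rule and the primary endpoint are unaffected. A row lost when the PDF was read cannot be fully excluded, but the table reads as complete.

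The change is worth making because the secondary safety result gains from it and data not collected prospectively are hard to recover.

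**What to change.** Add one row to the Section 10.54 table under Nervous System Disorders: Peripheral sensory neuropathy, marked X for Baseline and X for Each evaluation. Both marks are needed, because collecting grade 1 without an entry grade would count pre-existing neuropathy as new. Section 6.38 then makes the baseline grade mandatory without further edits, and 10.54 covers both forms named in Section 8.2.

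The cost is one more case report form item at each visit. The symptom check is already made before each infusion, so there is no new procedure, and no treatment rule changes.
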